| 15.4 Publications..... | 21 |
| 15.5 Investigator Responsibilities | 21 |

LIST OF ABBREVIATIONS

| | |
|--------------|-------------------------------------------------------------|
| AE | Adverse Event |
| CFR | Code of Federal Regulations |
| CRF | Case Report Form |
| DMC | Data Monitoring Committee |
| DSMB | Data Safety Monitoring Board |
| FDA | Food and Drug Administration |
| GCP | Good Clinical Practice |
| HIPAA | Health Insurance Portability and Accountability Act of 1996 |
| ICF | Informed Consent Form |
| ICH | International Conference on Harmonisation |
| IEC | Independent Ethics Committee |
| IRB | Institutional Review Board |
| PI | Principal Investigator |
| SAE | Serious Adverse Experience |

PROTOCOL SYNOPSIS

| | |
|-----------------------------------|----------------------------------------------------------------------------------------------------------------------------------------------------------------------------------------------------------------------------------------------------------------------------------------------------------------------------------------------------------------------------------------------------------------------------------------------------------------------------------------------------------------------------------------------------------------------------------------------------------------------------------------------------------------------------------------------------------------------------------------------------------------------------------------------------------------------------------------------------------------------------------------------------------------------------------------------------------------------------------------------------------------------------------------------------------------------------------------------------------------------------------------------------------------------------------------------------------------------------------------------------------------------|
| TITLE | ARJ C13 Urea Breath Test: An Open-Label, Comparator Group Study to Evaluate the equivalency of the ARJ C13 Urea Breath Test System to the predicate device ARJ Pylo Plus. |
| SPONSOR | ARJ Medical, Inc. |
| FUNDING ORGANIZATION | Gulf Coast Medical |
| NUMBER OF SITES | 3 |
| RATIONALE | 
Patients who are experiencing the effects of gastritis, which is an inflammation, irritation, or erosion of the lining of the stomach require an identification of the status and generation of urease in the stomach to provide a definitive diagnosis. Historically, this has been achieved via an upper endoscopy, where a thin tube containing a tiny camera, is inserted through your mouth and down into your stomach to look at the stomach lining. The doctor will check for inflammation and may perform a biopsy, a procedure in which a tiny sample of tissue is removed and then sent to a laboratory for analysis.
 
By ingesting a low dosage of C13 urea, the patients' exhaled breath is then measured to record the level of change of ^{13}C labeled urea detectable in a patient's breath. This is measured before and after the ingestion of the urea mixture. The exhaled breath is read by the analyzer which provides an immediate diagnoses and is non-invasive. Although other C13 Urea Test Kits and analyzers are in the market, the ARJ C13 Breath Test System is believed to be equivalent in functionality and will be manufactured in the U.S. which can provide a cost effective equivalent product.
 |
| STUDY DESIGN | Up to 3 centers, non-randomized, comparative study to compare the ARJ C13 Urea Breath Test System to the ARJ Pylo Plus rapid urease test. |
| PRIMARY OBJECTIVE | To demonstrate the ARJ C13 Breath Test System equivalency to the predicate ARJ Pylo Plus rapid urease test. |
| SECONDARY OBJECTIVES | None |
| NUMBER OF SUBJECTS | Test Group: Approximately 100 - 300 Study Subjects |
| SUBJECT SELECTION CRITERIA | 
Inclusion Criteria:
 
 • Male or Female \geq 18 years of age • Patients who are experiencing the effects of gastritis • Written informed consent (and assent when applicable) obtained from subject and ability for subject to comply with the requirements of the study. 
Exclusion Criteria:
 
 • Pregnant or lactating female • Study Subjects currently taking antibiotics • Presence of a condition or abnormality that in the opinion of the Investigator would compromise the safety of the patient or the quality of the data • Fasting required one hour prior to testing • Study Subjects shall not consume the following items prior to the test 
 ○ Mouthwash |

| | |
|----------------------------------------------------------------|----------------------------------------------------------------------------------------------------------------------------------------------------------------------------------------------------------------------------------------------------------------------------------------------------------------------------------------------------|
| | 
  Chewing gum  Carbonated beverages  Cigarette smoke  Acetone (to simulate the effect of ketone production that may result from some diets)  Alcohol |
| TEST PRODUCT, DOSE, AND ROUTE OF ADMINISTRATION | ARJ C13 Breath Test System will be administered one time during a one-time visit per Study Subject, according to the standard procedure described in the device's instructions. The administration shall be done orally followed by a series of specifically timed exhalations of the subject's breath. |
| CONTROL PRODUCT, DOSE AND ROUTE OF ADMINISTRATION | The ARJ Pylo Plus comparator product will be administered once at a follow-up appointment where the ARJ Pylo Plus test will be administered by the physician using a biopsy from the patient to test the presence of h. Pylori. |
| DURATION OF SUBJECT PARTICIPATION AND DURATION OF STUDY | 
Subjects will be on study for 2 days
 
Screening: up to 90 days
 
Test: 2 days
 
Reporting: 30 days
 
The total duration of the study is estimated to be 120 days. 3 months for subject screening and testing 1 month for final analysis and reporting.
 |
| CONCOMITANT MEDICATIONS | 
Allowed:
 
 • No exclusions with the requirement of fasting one hour prior to testing 
Prohibited:
 
 • Antibiotics |
| EFFICACY EVALUATIONS | The efficacy evaluations shall compare, per study subject, the results of the ARJ C13 Breath Test System to the results of the proven ARJ Pylo Plus test and the biopsy histology, rapid urease and culture tests. |
| PRIMARY ENDPOINT | 
 • Results of the test study patients' breath tests demonstrate acceptance criterion of $\geq 95\%$ to the ARJ Pylo Plus test readings. |
| SECONDARY ENDPOINTS | None |
| OTHER EVALUATIONS | None |
| SAFETY EVALUATIONS | 
When approximately 20% of patients have completed the study, an interim analysis for safety will be conducted.
 
Serious Adverse Events will be monitored on an ongoing basis throughout the study.
 |
| PLANNED INTERIM ANALYSES | When 20% of the study group patients have completed testing, analysis of the study results shall be processed and repeated monthly until the end of the study to evaluate the study progression. |

| | |
|---------------------------------------------------|------------------------------------------------------------------------------------------------------------------------------------------------------------------------------------------------------------------------------------------------------------------------------------------------------------------------------------------------------------------------------------------------------------------------------------------------------------------------------------------------------------------------------------------------------------------------------------------------------------------------------------------------------------------------------------------------------------------------------------------------------------------------------------------------------------------------------------------------------------------------------------------------------------------------------------------------------------------------------------------------------------------------------------------------------------------------------------------------------------------------------------------------------------------------------------------|
| STATISTICS Primary Analysis Plan | Each review of the subject(s) shall be recorded including documentation of status at selection and again during the comparative study test visit. The baseline reading and each subsequent breath test shall provide a complete series of breath readings per Study Subject. The analyzed breath readings shall be documented. The analysis of the results shall be graphed for the Study Group. This is to illustrate progression from start of the testing through the most recent day's tests of the study. At the end of the study, the results of the Study Group's ARJ C13 Breath Test System shall be compared to the results of the ARJ Pylo Plus, histology, rapid urease and culture results as compared per study subject. The Study Group's results shall be calculated and compared for equivalency. Adverse Events shall be documented by subject. All identified Adverse Events shall be given a level of adversity per Table 3- AE Severity Grading. The analysis of the results shall be graphed per subject and overall of all subjects per study group. This is to illustrate adversity from start of testing through the most recent testing per study group. |
| Rationale for Number of Subjects | The clinical studies for the ARJ C13 Urea Breath Test predicate device Pylo-Plus (K052708) included 100 study subjects. The recent clearance (May 2013) of the Exalenz Bioscience Ltd. Breath ID Hp System (K130524) included 79 pre-treatment study subjects. The rationale to use approximately 100 - 300 study subjects shows equivalency to the two (2) related clinical studies. |

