4 STUDY DESIGN

4.1 Study Overview

This will be up to three sites, open label, comparative trial. Approximately 100 – 300 (number) of subjects are planned. Each subject will be administered a single dose of study drug one time during a single visit. Evaluations will be taken at baseline and at a specified time during the testing session.

Screening data will be reviewed to determine subject eligibility. Upon patient's consent, subjects who meet all inclusion criteria and none of the exclusion criteria will be entered into the study.

The following testing regimens will be used:

- Using three independent sites, a total of 100-300 clinical samples are to be obtained from a population of symptomatic individuals who have been prescribed endoscopic examination for the detection of H.Pylori infection. The physician(s) will schedule test subjects per standard of care for an endoscopy procedure in which a gastric mucosal biopsy will be obtained. In addition to the physician's standard testing, the obtained tissue will also be used to perform the following tests:
 - Histology
 - Rapid Urease Test
 - Culture
- Experimental treatment ARJ C13 Urea Test dosage shall be a one-time dosage at time of initial testing.
- Comparator – ARJ Pylo Plus shall be a one-time test performed during a follow-up visit to examine the study subject's biopsy to determine the level of urease presence.
- Total duration of subject participation will be two visits. Total duration of the study is expected to be 4 months.

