5 CRITERIA FOR EVALUATION

5.1 Primary Efficacy Endpoint

Upon the completion of the four (4) months of testing, the test results of ARJ C13 Urea are expected to demonstrate equivalency to the ARJ Pylo Plus test results and equivalency to the results of the histology, rapid urease and culture tests results.

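### Nothing in the plan holds back the breath result until Pylo Plus is recorded, so the read behind the ≥95% criterion is open to a pull toward agreement

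*Combined protocol and SAP*

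**What the plan says.** **Open label.** The title calls the study "An Open-Label, Comparator Group Study to Evaluate the equivalency of the ARJ C13 Urea Breath Test System", and Section 4.1 says "This will be up to three sites, open label, comparative trial".

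**Breath result.** The Synopsis rationale, repeated in Section 2, says "The exhaled breath is read by the analyzer which provides an immediate diagnoses and is non-invasive". Section 8.3.3 has the Investigator or a designee keep a Study Activity Form for each subject, and the analyzer reading is one of its items.

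**Pylo Plus.** The Synopsis (Control Product) has the test "administered once at a follow-up appointment where the ARJ Pylo Plus test will be administered by the physician using a biopsy from the patient". Section 4.1 places the breath test at initial testing and says Pylo Plus "shall be a one-time test performed during a follow-up visit". The column headings of Appendix 1 give the same order. Section 8.3.2 lets the Investigator or a designee administer either product.

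**Success.** The Synopsis (Primary Endpoint) requires that the "breath tests demonstrate acceptance criterion of" at least 95% to the Pylo Plus readings. No other comparison has a number. Section 5.1 also expects "equivalency to the results of the histology, rapid urease and culture tests results", and the Primary Analysis Plan says the breath results "shall be compared to the results of the ARJ Pylo Plus, histology, rapid urease and culture results as compared per study subject".

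**Masking.** The available text has no rule that masks a reader, requires an independent reader or delays release of a result. The coded identifiers in Sections 14.5, 14.11 and 15 protect identity and do not conceal results.

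**The concern.** In a paired comparison of two tests, the later read should be made without knowledge of the earlier result. If the Pylo Plus reader knows the breath result and the read leaves any room for judgement, an uncertain Pylo Plus may be called to match. That moves discordant pairs into agreement, which favours the product under test on the one criterion that has a number.

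The plan also cannot repair this later. Section 14 promises a statistical analysis plan before the final data are analysed, but the reads will already have been made by then. No analysis can recover what an unmasked reader would have recorded without the breath result.

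**Working it through.** **1. Is the order such that the breath result could be known?** The passages conflict.

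- *Breath test first:* Synopsis (Control Product), Section 4.1, and the column headings of Appendix 1.
- *Unclear or contrary:* Section 10.1 schedules the study test for Visit 2, possibly on the same day. Section 10.2 titles Visit 2 as the study test. The Appendix 1 grid marks study drug administration at Visit 2 only.

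If the breath test comes first, the reader could know its result. If Pylo Plus is read first, the later result is an analyzer reading and this bias is much less likely.

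**2. Is there a plan figure to reproduce?** No. The sample size of about 100 to 300 rests on the sizes of two other studies (100 and 79 subjects). No expected agreement, error rate or power is given, so no formula can return it.

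**3. How much could a pull matter?** This part is illustrative. Inputs:

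- N = 100 and N = 300, the ends of the planned range.
- The criterion is read as observed overall agreement of at least 95%, that is 95 of 100 or 285 of 300. The plan does not define the statistic, so this is an assumption.
- *a* = true agreement. Assumed, ranged from 85% to 97%.
- *f* = share of discordant Pylo Plus reads pulled to the breath result, with concordant reads unchanged. Assumed at 0, 10% and 25%.

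Observed agreement: p = a + f(1 − a). For example, with a = 0.92 and f = 0.25, p = 0.92 + 0.25 × 0.08 = 0.94.

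Chance of passing: P(X ≥ 0.95N) with X binomial(N, p), computed exactly.

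| True agreement | f = 0: N=100 / N=300 | f = 10%: N=100 / N=300 | f = 25%: N=100 / N=300 |
|---|---|---|---|
| 85% | 0.2% / <0.1% | 0.5% / <0.1% | 2.6% / <0.1% |
| 90% | 5.8% / 0.1% | 10.5% / 0.7% | 23.1% / 5.6% |
| 92% | 18.0% / 2.9% | 26.6% / 8.1% | 44.1% / 27.9% |
| 94% | 44.1% / 27.9% | 54.4% / 44.4% | 70.5% / 72.1% |
| 97% | 91.9% / 98.0% | 94.6% / 99.2% | 97.4% / 99.9% |

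A very small pull does little. With a = 92% and f = 2%, p = 0.9216 and the chance of passing is 19.5% (N = 100) or 3.6% (N = 300), against 18.0% and 2.9% with no pull.

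**4. How large a pull lifts expected agreement to 95%?** Solve a + f(1 − a) = 0.95, which gives f = (0.95 − a)/(1 − a):

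- a = 85%: 0.10/0.15 = 67%
- a = 90%: 0.05/0.10 = 50%
- a = 92%: 0.03/0.08 = 37.5%
- a = 94%: 0.01/0.06 = 17%

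The effect is therefore material mainly when true agreement is a few points below 95%. A larger sample does not remove it: at 94% with a 25% pull, 300 subjects pass about as often as 100.

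**The case against.** The strongest reply is that the mechanism is assumed. A pull needs a reader who knows the breath result and a read that leaves room for judgement, and the documents establish neither. The causes of wrong results that they do name are patchy biopsy sampling (Section 1), other urease-producing organisms and achlorhydria (Section 2.1.1), none of which is reader judgement. The model treats every discordant read as equally movable, although a biopsy that missed the organism may give a plainly negative read. The visit order is also unsettled, and the probabilities rest on two assumed quantities and an assumed form of the criterion. All of this stands. It makes the table a sensitivity exercise and not an estimate of bias.

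A reader might go further and infer that the physician sees the breath result, that one person performs both tests, or that the trial's agreement figure will be inflated. The documents support none of these. Section 8.3.2 names a role, not a person, and Section 8.3.3 lists the analyzer reading on a form without saying who consults it or when.

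A second reply is that Section 5.1 also expects equivalence to histology, rapid urease and culture, so a pulled Pylo Plus read could show up as disagreement with those tests. This stands in part. The check is partial because no section masks those readers either, and the 95% figure is tied to Pylo Plus alone.

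Open-label status is not an answer. Every subject has both tests, and holding one result back from one reader for a time is compatible with an open-label study.

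**Conclusion.** The point holds as an unclosed opportunity for bias, not as a demonstrated bias. If the breath test comes first, the plan leaves the deciding read unprotected, and any pull toward the breath result raises agreement on the only numeric criterion. Under the assumptions above, a pull of 10% to 25% of discordant reads raises the chance of passing from 18% to between 27% and 44% (N = 100), or from 3% to between 8% and 28% (N = 300), when true agreement is 92%. The change is small at 85% and at 97%. The share pulled, the true agreement, the reader's knowledge, the subjectivity of the read and the form of the criterion are all assumptions.

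The sponsor should make the change because it costs little and can work only before the reads are made. Confidence is medium, given how much the documents leave unstated.

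**What to change.** 1. **Visit order.** Reconcile Sections 4.1, 10.1, 10.2 and Appendix 1 first. If Pylo Plus turns out to be read first, the rule below is met by the order itself.
2. **Section 4.1.** State that the Pylo Plus result is read and entered before the breath result is disclosed to the person reading Pylo Plus.
3. **Section 8.3.3.** Record the analyzer reading on a separate sheet, kept from that person until the Pylo Plus result is entered.
4. **Section 14.5.** State that the Investigator's review and verification of a subject's data follows entry of both results. Otherwise a physician who is also the Investigator could see the breath result through that duty.

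This is a timing rule and does not by itself require a separate reader. It costs a few sentences and one sheet, with no new test or procedure. The downsides are real. The breath result reaches the physician later, by up to the interval between visits, which the plan does not state. At a site where one person would do both tests, the designee already allowed by Section 8.3.2 would have to run and record the breath test.

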12.2 Replacement of Subjects

Subjects who withdraw from the study will be replaced.

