14 STATISTICAL METHODS AND CONSIDERATIONS

Prior to the analysis of the final study data, a detailed Statistical Analysis Plan (SAP) will be written describing all analyses that will be performed. The SAP will contain any modifications to the analysis plan described below.

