14.1 Data Sets Analyzed

All eligible patients who are randomized into the study and receive at least one dose of the study drug (the Safety Population) will be included in the safety analysis.

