14.3 Interim Analysis

Interim study analysis shall be performed after the initial two weeks of testing and again at the end of one month of testing. Analysis will continue on a monthly basis until the end of the study.

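### The only numeric success rule, 95% against Pylo Plus, names no agreement measure or interval and pools positives with negatives, so a pass can hide poor positive agreement when positives are few

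*Combined protocol and SAP*

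**What the plan says.** The synopsis, under Primary Endpoint, requires that the breath test results "demonstrate acceptance criterion of $\geq 95\%$ to the ARJ Pylo Plus test readings". No other efficacy figure serves as a pass mark anywhere in the protocol.

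The synopsis Primary Analysis Plan adds only this: "The Study Group's results shall be calculated and compared for equivalency". Section 5.1 expects equivalency to Pylo Plus and also "equivalency to the results of the histology, rapid urease and culture tests results", with no number for any of these comparisons. Section 14 describes a safety population, demographic summaries, interim looks and a sample size based on two earlier device studies. It names no agreement statistic, confidence interval or margin, and no analysis by Pylo Plus result.

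Two things can be read from the text. The comparison is made within each subject (synopsis, Efficacy Evaluations and Primary Analysis Plan). The breath test is qualitative (Section 1), and the synopsis description of the control product has Pylo Plus testing for the presence of *H. pylori*. Together these point to paired positive/negative results. The planned size is about 100 to 300 subjects. The expected share of Pylo Plus positives is not given, and no minimum number of positives is set.

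**The concern.** The 95% rule carries the primary objective. A single pooled percentage is dominated by whichever Pylo Plus group is larger. If most subjects are negative, a breath test that misses many Pylo Plus positives can still exceed 95% because it agrees on the negatives. The study would then declare equivalence while saying little about agreement in the subjects whom Pylo Plus identifies as infected.

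The rule also does not say whether 95% is an observed value or a confidence bound. The same data can therefore pass on one reading and fail on the other.

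**Working it through.** **Inputs.** From the protocol: threshold 95%, N = 100 to 300, paired results per subject. Assumed, because the documents do not give them: Pylo Plus positives at 10%, 20%, 30% or 40% of subjects; true positive agreement of 75%; true negative agreement of 99% or 98%. The plan offers no derivation of the 95% or of the sample size, so there is no stated figure to reproduce.

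**Step 1: discordance allowed.** N − 0.95N gives 100 − 95 = 5 discordant subjects, or 300 − 285 = 15. They may be breath-negative/Pylo-positive, the reverse, or a mixture.

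**Step 2: lowest positive agreement compatible with a bare pass.** If every discordance falls among the positives, positive agreement = (positives − allowed discordances) / positives.

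| Positives | N=100 | N=300 | Positive agreement | Exact 95% interval, N=100 | Exact 95% interval, N=300 |
|---|---|---|---|---|---|
| 10% | 5/10 | 15/30 | 50% | 18.7–81.3% | 31.3–68.7% |
| 20% | 15/20 | 45/60 | 75% | 50.9–91.3% | 62.1–85.3% |
| 30% | 25/30 | 75/90 | 83.3% | 65.3–94.4% | 74.0–90.4% |
| 40% | 35/40 | 105/120 | 87.5% | 73.2–95.8% | 80.2–92.8% |

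**Step 3: how often a weak test passes.** Step 2 is a worst case, so the probability matters too. With the number of positives fixed at share × N, total agreements = Binomial(positives, 0.75) + Binomial(negatives, negative agreement). The test passes if the total is at least 95 of 100 or 285 of 300. Each cell gives N=100 / N=300.

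| Positives | Negative agreement 99% | Negative agreement 98% |
|---|---|---|
| 10% | 89% / 96% | 75% / 79% |
| 20% | 46% / 31% | 33% / 14% |
| 30% | 14% / 1.5% | 9% / 0.5% |
| 40% | 3% / under 0.1% | 2% / under 0.1% |

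At 10% positives the larger study passes the weak test more often, because expected overall agreement is above the threshold: 0.10 × 0.75 + 0.90 × 0.99 = 96.6%. At 20% it is 0.20 × 0.75 + 0.80 × 0.99 = 94.2%, below the threshold, and the larger study helps.

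**Step 4: sampling error.** A bare pass has an exact two-sided 95% lower bound of 88.7% (95/100) or 91.9% (285/300). If the rule were meant as a lower bound of at least 95%, it would need 100/100 or 293/300. Under the point-estimate reading, a test with true overall agreement of 93% passes 29% of the time at N=100 and 10% at N=300.

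**Step 5: denominator, as illustration only.** If 5 of 100 subjects lacked a usable pair (an assumed rate), 91 agreements would be 91/95 = 95.8% of pairs but 91% of all subjects.

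**The case against.** The strongest reply is that the meaning is plain enough. Comparison per subject and a qualitative device imply observed overall agreement among subjects with both readings, and a point-estimate criterion is a legitimate design choice. This largely stands. It is why the calculation uses that reading, and why the denominator is treated as missing detail. It does not answer the pooling of positives and negatives, which is a feature of that very reading.

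A second reply is that nothing in the protocol supports 10% positives. The subjects are symptomatic and referred for endoscopy to detect *H. pylori*, and both kinds of discordance are likely: Section 1 says biopsy methods can give false negatives, and Section 2.1.1 says the breath test can give false positives. Both use up the 5% allowance. This also stands, and it limits the size of the concern. It does not remove it, since no share or minimum number of positives is planned.

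A third reply is that the SAP will settle the measure: "Prior to the analysis of the final study data, a detailed Statistical Analysis Plan (SAP) will be written". It may, but it is not among the documents, and the rule in the protocol stays incomplete without it.

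Three stronger readings are tempting and not supported:
- A reader might infer from the repeated interim analyses that the measure could be chosen after seeing results. The stated purpose of those looks is to follow study progress, and no efficacy decision or stopping rule is attached to them.
- A reader might infer from references to a level of urease or *H. pylori* (Sections 3.1 and 4.1) that the readings are not positive/negative. The text as a whole favours positive/negative results.
- A reader might infer that the denominator is open enough to reverse the conclusion. The example in Step 5 rests on an assumed missing rate and on counting missing pairs as disagreements, which the protocol nowhere suggests. Section 12.2 also says "Subjects who withdraw from the study will be replaced", which would reduce missing pairs.

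**Conclusion.** The concern holds in a bounded form. The protocol's only numeric success rule leaves the agreement measure and interval unstated and pools Pylo Plus positives with negatives. Read naturally, it can be met with positive agreement as low as 50% at 10% positives, 75% at 20%, 83% at 30% and 87.5% at 40%.

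The practical risk depends on the share of positives, which is an assumption throughout. It is large near 10%. At 20% it is moderate and depends on how good negative agreement is. At 30% it is modest for N=100 and slight for N=300, and at 40% it is small. It would be wrong to say that a pass generally conceals poor positive agreement. Separately, at any share of positives, a bare pass leaves true overall agreement below 90% not excluded at N=100 (lower bound 88.7%).

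All of this concerns agreement with Pylo Plus. Because the protocol says biopsy methods can miss infection, discordance is not by itself evidence that the breath test is wrong.

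**What to change.** Change the synopsis Primary Endpoint and Primary Analysis Plan, and Section 5.1, before any results are first analysed:

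1. State that the 95% is observed overall agreement of positive/negative results among subjects with both readings. Report the number of missing or unreadable results. Keep the 95% as a necessary condition for success.
2. Make positive and negative percent agreement with Pylo Plus co-reported primary results, each with counts and a two-sided 95% exact or Wilson interval.
3. Limit the equivalence conclusion to what those intervals support. Do not claim equivalence for Pylo Plus positives from the pooled percentage alone.
4. Report the histology, rapid urease and culture comparisons in the same form, as supportive results.

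This is wording and reporting on results already planned per subject, so no new data are needed. The cost is a more cautious claim: even with no misses, the exact lower bound for positive agreement is 69.2% for 10/10 and 83.2% for 20/20.

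A separate threshold on positive or negative agreement is left to the sponsor because it has its own cost. Requiring 95% observed on each would fail a test with 98% true agreement on both sides 21% of the time at N=100 with 10 positives, and 12% at N=300 with 30.
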